7.3.3 Labelling

The content of the labelling will be in accordance with the Good Manufacturing Practices and the local specifications and requirements.

The cardboard cartons for period D1-D14 and for period D14-D42 will carry detachable labels (flag label) bearing the protocol number, treatment number and the treatment period (D1-D14) or (D14-D42). These labels will be torn off by the person dispensing the medication to the patient, and will be stuck in the space provided in the CRF in order to record the dispensing procedure.

7.3.4 Preservation and Storage

The investigational products will be provided by the sponsor to the study site pharmacist. An acknowledgment of receipt will be completed by the pharmacist and returned to the sponsor.

The investigational products will be stored under the supervision of a pharmacist approved for the study under suitable safety conditions ensuring proper storage, at room temperature (below 25°C) in a dedicated air-conditioned room. This room is locked and access controlled.

The investigational products will be only used following the specifications detailed in this protocol, and only for patients having been randomized by the investigator.

7.3.5 Dispensing and accountancy of investigational products supplies

The investigational product should only be dispensed only under the supervision of a physician approved for the study. The investigator (or delegate) is responsible for dispensing the investigational products to the patients who are included in the study. The investigational products must not be administered to patients who are not included in the study.

A specific accountancy form provided by the Sponsor must be kept current and must identify the subject number/the number of the product dispensed, and the amount of product dispensed to and returned by each subject at each visit, with the corresponding dates.

All products supplies (empty containers, as well as partly used and unused products must be available for inspection at every monitoring visit. The CRA or sponsor delegate should verify the investigational site's products accountability records against record of administrated doses in the CRF.

All products (wasted and unused) must be returned by the patients to the investigator at each visit and by the investigator to the sponsor at the end of the study.

Compliance with the investigational product will be checked at each visit by the investigator and reported on the Study Drug Form. In order to verify investigational product compliance, patients will be questioned during the protocol visits about their compliance. In addition, the patients will also have to report information about his compliance on a diary during the treatment period. This diary will not be recorded onto database.

7.4 Product allocation – Randomization - Blinding

Not applicable. All patients will receive the same product.

7.5 Treatment(s) and associated product(s)

Cf 7.5.4

7.5.1 Authorized medication(s) and treatment(s)

Any concomitant medication at inclusion of the subject into the study must be reported on the source document and in the study CRF at the initial visit and will be taken into consideration by the Investigator deeming study eligibility.

Any modification on these medications during the study *must* be reported on the source document and in the study CRF.

Use of any concomitant medication will be recorded in the CRF with the following information:

- Indication for use of the treatment;
- Name of the drug, type of formulation, and unit strength;

- Dose administered;
- Duration of treatment (start and stop date).

7.5.2 Non-authorized medication(s) and treatment(s)

The treatments specified in paragraph 6.2. are not authorized during all the duration of whole study period. More generally, patients will not be allowed to take any medication which might interfere with the efficacy or interpretation of the study end point evaluations specified in this protocol, unless the subject elects to withdraw from the study. If there is any question whether a particular concomitant medication is allowed, the Investigator should consult the Sponsor.

7.5.3 Rescue treatment

If case of adverse reaction affecting subject well-being, the investigator is authorized to interrupt the use of the investigational product and prescribe to the subject a rescue treatment/medication.

The adverse medical event will be recorded in the subject's CRF, including details on rescue medication, and will be managed according to section 7.5.1.

7.5.4 Auxiliary product used but not studied

During the run-in period, from screening visit to D1, Physiol[®] will be given to the patients (artificial tears without preservative).

Name: Physiol[®]

Composition: NaCl 0.9%

Form: sterile solution

Administration route: ocular route

AMM: 9093032H

Date AMM: 13/10/1993

Dosage: one drop in each eye 3 to 6 times daily

8 EFFICACY ASSESSMENT

[figure not shown]
8.1 Description of efficacy assessment parameters

8.1.1 Primary efficacy variable

The primary efficacy variable will be the symptomatology within the last 48 hours on a VAS

Symptomatology evaluation (global evaluation for both eyes) will be assessed by the patient at each visit according to the following:

“Please mark a vertical line on the horizontal line, indicating your level of ocular discomfort due to ocular dryness within the last 48 hours”. VAS will be a 100 mm line: 0 mm = No discomfort, 100 mm = Maximal discomfort.

[figure not shown]

8.1.2 Other efficacy variables

8.1.2.1 Conjunctival hyperaemia using Mac Monnies photographic scale

The conjunctival hyperaemia will be assessed using the Mac Monnies photographic scale (Figure 1). This test will be performed at each visit.

Figure 1 – Mac Monnies photographic scale

This test will be performed in both eyes at each visit. The value at D1 will be the baseline value.

[figure not shown]
[figure not shown]

[figure not shown]
[figure not shown]

[figure not shown]
[figure not shown]

8.1.2.2 *Global ocular staining (Oxford scale)*

Cornea and conjunctiva staining will be assessed with a slit lamp after instillation of unpreserved fluorescein in the examined eye. In order to optimize the fluorescein staining signal without any masking by the fluorescence quenching effect, 1 drop of fluorescein will be instilled in the examined eye.

Cornea and conjunctiva staining is represented by punctate dots on a serie of panels (A-E). Staining ranges form 0-5 for each zone and from 0-15 for the total exposed inter-palpebral conjunctiva and cornea. The dots are ordered on the log scale (Oxford scale) below (Figure 2):

The Oxford score will be measured at each visit in both eyes. The value at D1 will be the baseline value.

Figure 2 – Oxford 0-15 grading scheme

OXFORD SCHEME (15 POINTS)						
Panel RE			Grade Criteria	Panel LE		
A			0 Equal to or less than panel A	A		
B			I Equal to or less than panel B, greater than A	B		
C			II Equal to or less than panel C, greater than B	C		
D			III Equal to or less than panel D, greater than C	D		
E			IV Equal to or less than panel E, greater than D	E		
>E			V Greater than E	>E		
Temporal bulbar conjunctiva	Corneal area	Nasal bulbar conjunctiva	USE GRADE 0 TO 5 FOR EACH AREA	Nasal bulbar conjunctiva	Corneal area	Temporal bulbar conjunctiva
__	__	__		__	__	__
TOTAL GRADE : __ __				TOTAL GRADE : __ __		

8.1.2.3 *Van Bijsterveld score*

The global ocular staining will also be assessed by the Van Bijsterveld score from the lissamine green coloration.

This test will be performed in both eyes at each visit. The value at D1 will be the baseline value.

Impregnated paper will be used for staining, put in the same area as paper strip for Schirmer test. Reading will be performed between 1 and 4 minutes after stain to optimize staining (a chronometer will be used). The eye will be then examined at the slit lamp. Ocular surface will be observed starting with a low illumination possibly under red light (intense or bright illumination will diminish contrast and underestimate the degree of staining). The level of light may be increased until the staining is the most visible.

[figure not shown]
[figure not shown]
The evaluation of the test will be performed according to the Van Bijsterveld score (Figure 3). The corneo-conjunctival exposed surface is separated in 3 parts: nasal bulbar conjunctive, corneal area, and temporal bulbar conjunctive. The following score will be attributed to each of these parts with the help of a visual figure representing each degree of staining:

- (0) = No coloration.
- (1) = Some punctuations.
- (2) = Well defined punctuations.
- (3) = Total coloration.

The total score is the addition of the scores obtained in the 3 parts (nasal, corneal and temporal).

Figure 3 – Van Bijsterveld score

Assessment should be made between 1 and 4 minutes after Lissamine staining.

RE			LE		
Temporal bulbar conjunctiva	Corneal area	Nasal bulbar conjunctiva	Nasal bulbar conjunctiva	Corneal area	Temporal bulbar conjunctiva
					
A	B	C	C	B	A
0 1 2 3	0 1 2 3	0 1 2 3	0 1 2 3	0 1 2 3	0 1 2 3
   	   	   	   	   	   
Global Score = A+B+C =			Global Score = C+B+A =		

Score the **punctuation** using the scale of 0 to 3:

0 = No coloration.

1 = Some punctuations.

2 = Well defined

punctuations. 3 = Total coloration.

8.1.2.4 Ocular Surface Disease Index (OSDI)

The impact of the disease on the patient's daily activities will be assessed by the Ocular Surface Disease Index described in Figure 4. It will be measured on D1, D14 and D42

Figure 4 – Ocular Surface Disease Index

Have you experienced any of the following during the last week?	All of the time	Most of the time	Half of the time	Some of the time	None of the time
1. Eyes that are sensitive to light?	4	3	2	1	0
2. Eyes that feel gritty?	4	3	2	1	0
3. Painful or sore eyes?	4	3	2	1	0
4. Blurred vision?	4	3	2	1	0
5. Poor vision?	4	3	2	1	0

Subtotal score for answers 1 to 5

Have problems with your eyes limited you in performing any of the following during the last week?	All of the time	Most of the time	Half of the time	Some of the time	None of the time	N/A
6. Reading?	4	3	2	1	0	N/A
7. Driving at night?	4	3	2	1	0	N/A
8. Working with a computer or bank machine (ATM)?	4	3	2	1	0	N/A
9. Watching TV?	4	3	2	1	0	N/A

Subtotal score for answers 6 to 9

Have your eyes felt uncomfortable in any of the following situations during the last week?	All of the time	Most of the time	Half of the time	Some of the time	None of the time	N/A
10. Windy conditions?	4	3	2	1	0	N/A

11. Places or areas with low humidity (very dry)?	4	3	2	1	0	N/A
12. Areas that are air conditioned?	4	3	2	1	0	N/A

Subtotal score for answers 10 to 12

Add subtotals A, B, and C to obtain D
(D = sum of scores for all questions answered)

Total number of questions answered
(do not include questions answered N/A)

$$\text{OSDI} = \frac{\text{Sum of scores (D)} \times 25}{\text{Number of questions answered (E)}} = \text{_____} = \text{_____}$$

8.1.2.5 Schirmer test without anaesthesia

The Schirmer test will be conducted in a dimly lit room. Whilst the patient looks upwards, the lower lid will be drawn gently and temporally downwards. The rounded bent end of a sterile strip will be hooked in the lower conjunctival sac over the temporal one-third of the lower eyelid margin. After 5 minutes have elapsed, the tear front will be measured.

This test will be performed in both eyes at each visit. The value at D1 will be the baseline value.

8.1.2.6 Tear Break-Up Time (TBUT)

The TBUT will be done at each visit. The value at D1 will be the baseline value.

The tear break-up time will be measured 3 times rapidly after the instillation of one drop of fluorescein. The TBUT value analyzed will be the sum of the 3 measurements.

This test will be performed in both eyes at each visit. The value at D1 will be the baseline value.

8.1.2.7 Ocular symptoms

Patient will be asked: ““How do you judge the severity of your following ocular symptoms within the last 48 hours?””

The severity of the following ocular symptoms will be assessed at each visit: burning/irritation, stinging/eye pain, itching/pruritus, eye dryness feeling, tearing, foreign body sensation, light sensitivity as follows:

0 = Absent (absent)

1 = Mild, present but not disturbing (présent mais non gênant)

2 = Moderate, disturbing, but not limiting with daily activities (gênant, mais ne limitant pas les activités quotidiennes)

3 = Severe, very distressing and interfering with daily activities (très gênant et limitant les activités quotidiennes)

The ocular symptoms will be assessed in global for both eyes at each visit. The value at D1 will be the baseline value.

8.1.2.8 Soothing sensation

The soothing sensation felt by the patient within 15 min after IP instillation after 14 and 42 days of treatment will be assessed according to the following scale:

(0) = None,

(1) = Mild,

(2) = Moderate,

(3) = Important

The soothing sensation will be assessed in global for both eyes at each visit post-baseline.

8.1.2.9 Ocular efficacy assessment by the investigator

The evaluation of the overall efficacy of investigational product will be assessed by the patient and by the investigator on D14 and D42, in global for both eyes, using the following rating scale:

- (3) = Very satisfactory,
- (2) = Satisfactory,
- (1) = Not very satisfactory,
- (0) = Unsatisfactory.

8.2 Methods and calendar for measuring, collecting and analysing efficacy assessment parameters

Study procedures	D1 (Baseline)	Day 14 (+/- 1 day)	Day 42 (+/- 5 days)
OSDI score	X	X	X
Conjunctival hyperaemia	X	X	X
Schirmer test	X	X	X
TBUT	X	X	X
Oxford 0-15 score	X	X	X
Van Bijsterveld score	X	X	X
Symptomatology evaluation (VAS)	X	X	X
Ocular symptoms	X	X	X
Soothing sensation		X	X
Ocular efficacy assessment by the investigator		X	X

9 ASSESSMENT OF SAFETY

9.1 Description of the safety assessment parameters

9.1.1 Adverse events

Ocular and systemic AEs will be reported at each contact with the patient (visits on D1, D14 and D42).
The handling of adverse events is detailed in section 9.3.

9.1.2 Far best-corrected visual acuity in both eye

Far Best-corrected visual acuity will be measured at the screening visit (visit #1) and on Day 42 visits with the patient's best correction using a Snellen chart.

The value at screening visit will be the baseline value.

9.1.3 Ocular tolerance assessment by the patient and the investigator

The ocular tolerance of the investigational product will be assessed on D14 and D42 by the patient and the investigator, in global for both eyes, using the following rating scale:

- (3) = Very satisfactory,
- (2) = Satisfactory,
- (1) = Not very satisfactory,
- (0) = Unsatisfactory.

9.1.4 Ocular symptoms upon instillation

Ask the patient:

“Have you felt any ocular discomfort/unusual sensation UPON INSTILLATION since the last visit?”

« Avez-vous ressenti une gêne/sensation oculaire inhabituelle à l'instillation depuis la dernière visite ?» If the answer is yes, a table regrouping the functional ocular signs will have to be completed.

burning/irritation, stinging/eye pain, itching/pruritus, eye dryness feeling, foreign body sensation, and other symptoms will be graded by the patient.

according to the following severity scale and with their duration:

(0) = Absent.

(1) = Mild: present but not disturbing.

(2) = Moderate: disturbing, but not limiting with daily activities.

(3) = Severe: Very distressing and interfering with daily activities.

The ocular symptoms upon instillation will be assessed in global for both eyes at each visit post-baseline.

9.2 Foreseen schedule for measuring, collecting and analysing these parameter

Study procedures	Screening visit (D-14/D-10)	D1	Day 14 (± 1 day)	Day 42 (± 5 days)
Ocular symptoms upon instillation			X	X
Far Best Corrected Visual Acuity (FBCVA) in both eyes	X			X
Adverse events		X	X	X
Ocular tolerance assessment by the investigator			X	X
Ocular tolerance assessment by the patient			X	X

9.3 Procedures for collection, registration and notification of adverse events

9.3.1 Definitions

9.3.1.1 Definition of adverse event (AE)

Adverse Event (AE): any untoward medical events that occurs in a patient who has accepted the participation in the study and which does not necessarily have a causal relationship with the Investigational Product (IP).

An AE can therefore be any unfavourable and unintended sign (including abnormal laboratory finding), symptom, or disease temporally associated with the use of an IP, whether or not related to the product.

An AE may include, but is not limited to:

- A new illness
- Worsening of a sign or symptom of the condition under treatment or of a concomitant illness
- An effect of the IP (Test product or comparator product)
- An effect of an auxiliary product
- Event unrelated to participation in the clinical study
- A combination of one or more of these factors

Adverse Drug Reaction (ADR): untoward and unintended response in a patient to the IP which is related to any dose administered to that patient.

Unexpected ADR: An adverse reaction is unexpected when the nature and severity is not consistent with the information about the medicinal product set out in the investigator's brochure relating to the trial in question.

All AEs, including intercurrent illnesses, occurring during the study will be documented in the e-CRF. Concomitant illnesses, which existed prior to entry into the study, will not be considered AEs unless they worsen during the treatment period. Pre-existing conditions will be recorded in the CRF.

9.3.1.2 Definition of a Serious Adverse Event (SAE) or Reaction

Regarding the clinical study design and the regulatory requirements, A **serious Adverse event** is:

Any untoward medical occurrence or effect that at any dose results in:

- ✓ Death of the patient
- ✓ The condition of the patient is life-threatening

LABORATOIRES THEA	Protocol # LT2769-001/ 17E1044	Final Version 2.0 Date: 13/11/2017	Confidential Page 53/75
-------------------	--------------------------------	---------------------------------------	----------------------------

- ✓ The patient requires hospitalisation, or a prolongation of existing hospitalisation
- ✓ Persistent or significant disability or incapacity
- ✓ A congenital anomaly or birth defect
- ✓ Other medically-important events (*pregnancy, accidental or voluntary overdose, cancer or any other unfavourable medical event which is not fatal, life-threatening, and does not require hospitalisation, but requires urgent and intensive treatment*).

Medical and scientific judgment should be exercised in deciding whether a case is serious and whether expedited reporting is appropriate.

9.3.1.3 Definition of a new event

New events related to the conduct of a trial or the development of an IMP likely to affect the safety of patients, such as: — a serious adverse event which could be associated with the trial procedures and which could modify the conduct of the trial, — a significant hazard to the subject population such as lack of efficacy of an IMP used for the treatment of a life-threatening disease, — a major safety finding from a newly completed animal study (such as carcinogenicity), — a temporary halt of a trial for safety reasons if the trial is conducted with the same investigational medicinal products in another country by the same sponsor.

9.3.1.4 Definition of the severity of an Adverse Event/Reaction

The intensity of each AE must be assessed by the Investigator using one of the following categories, and recorded in the e-CRF:

1 = MILD Event results in mild or transient discomfort, not requiring intervention or treatment and does not interfere with the patient daily activities.

2 = MODERATE Event results in sufficient discomfort, may require an additional treatment, but does not interfere with the patient's daily activities.

3 = SEVERE Event results in significant symptoms, may require an additional treatment, or a modification of this treatment (or hospitalisation) and may interfere with the patient's daily activities.

Caution: The term “severe” is used to describe the intensity (severity) of the event. This means it is not the same as “serious” used to describe the seriousness of serious adverse event (SAE) which is based on patient/event outcome or action criteria usually associated with events that pose a threat to a patient's life

or functioning (see section 6.6.8.4 “Reporting Serious Adverse Events” for having the definition of an SAE).

9.3.1.5 Relationship with the tested product

The investigator will assess the causality/relationship between the IP and the AE and record that assessment in the e-CRF based on the following definitions (only one answer possible):

- 1 RELATED** The adverse event is related to the tested product and cannot be reasonably explained by other factors (*e.g: concomitant therapy, patient condition, and/or other intervention*).
- 2 NOT RELATED** A simultaneous disease, a simultaneous treatment or any other known condition clearly triggers the adverse

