3.4 Summary of potential benefits and risks for the patients

The literature analysis points out the clinical benefits of the three main ingredients of T2769 in the treatment of DED. Clinical studies on sodium hyaluronate 0.15% (Hyabak®), trehalose 3% (Thealoz®) and the combination of sodium hyaluronate 0.15% and trehalose 3% (Thealoz Duo®) confirmed that these agents are valuable options in the management of DED (*i.e.*, allowing

protection, hydration and lubrication of the eye, and improving ocular symptoms and signs) (Ramothe et al., 2013; Brjesky et al., 2014; Schmidl et al., 2015; Pinto-Bonilla et al., 2015; Chiambaretta et al., 2017). The treatment of dry eye patients with NAAGA 4.9% was also shown to significantly decrease the expression of inflammation markers and to improve ocular symptoms and overall comfort (Brignole-Baudouin et al., 2009).

As regards safety, the combination of sodium hyaluronate 0.15% and trehalose 3% (Thealoz Duo®) is well tolerated and safe for the treatment of DED. In a recent clinical study conducted in DED patients (Chiambaretta et al., 2017), the incidence of ocular AEs was lower for Thealoz Duo® (1 patient, 1.9%) than for the reference product Vismed® (sodium hyaluronate 0.18% eye drops) (7 patients, 13.2%). The ocular AE (moderate viral conjunctivitis) experienced by the patient in the Thealoz Duo® group was not considered to be treatment-related by the investigator. No serious adverse event was reported in this study. For NAAGA (at 4.9%), among the 53 dry eye patients included in the Brignol-Baudouin's study (Brignole-Baudouin et al., 2009), one patient reported worsening of an existing blepharitis (for which the relation to treatment was considered doubtful by the investigator) and another patient reported hyperaemia, burning sensation and lid swelling (considered as possibly related to treatment) in the Naabak® group. No serious adverse event was reported in this study.

Currently, the product information mentions the following side effects for Thealoz Duo® and Naabak® (NAAGA at 4.9%), respectively:

- *"You may have mild eye irritation, although is very unusual"* (Thealoz Duo® IFU, 2015)
- *"Possibility of brief sensation of burning or stinging at instillation"* (Naabak SmPC, 2016)

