12.3.3 Safety Analyses

Safety endpoints will be analysed in the Safety Set.

Safety analysis will be based on the following criteria:

- Ocular symptoms upon instillation: : burning/irritation, stinging/eye pain, itching/pruritus, eye dryness feeling, foreign body sensation, and other symptoms will be graded by the patient.at D14 and D42
- Far best corrected visual acuity assessment at D42
- Global ocular tolerance assessed by the investigator at D42
- Global ocular tolerance assessed by the patient at D42
- Ocular and systemic adverse events (AE)

The adverse events will be coded using the MedDRA dictionary and described according to MedDRA Preferred Term (PT) and primary System Organ Class (SOC).

The number and percentage of patients with at least one adverse event will be summarized for all AEs, study product-related AEs, serious AEs, and AEs leading to study withdrawal.

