7.5.1 Summary of adverse events

Separate summaries of treatment-emergent ocular and systemic AEs will be performed presenting the number and percentages of patients experiencing at least one:

- AE,
- Serious AE (SAE),

- Drug-related AE (i.e. related or missing relationship with the IP),
- Drug-related SAE (i.e. related or missing relationship with the IP),
- AE leading to premature study withdrawal.

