7.5.2 Details of adverse events

Separately for ocular and systemic AEs, following descriptions will be performed:

- Number and percentage of patients experiencing at least one TEAEs as well as the number of TEAEs by SOC and PT. The same summary table will be performed for SAEs, drug-related AEs, drug-related SAEs and AEs leading to premature treatment withdrawal,
- Number and percentage of patients experiencing at least one TEAEs as well as the number of TEAEs by SOC, PT and severity,
- Number and percentage of patients experiencing at least one TEAEs as well as the number of TEAEs by SOC, PT and relationship with IP.

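### Protocol 9.3.1.5: the two causality categories leave out events of uncertain cause, so drug-related AE and SAE counts can be understated

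*Protocol*

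**What the plan says.** Protocol 9.3.1.5 has the investigator judge the relationship of each AE to the product, with "only one answer possible". Two categories are listed:

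- RELATED: "The adverse event is related to the tested product and cannot be reasonably explained by other factors". The examples of other factors are concomitant therapy, the patient's condition and other interventions.
- NOT RELATED: "A simultaneous disease, a simultaneous treatment or any other known condition clearly triggers the adverse". The sentence breaks off there in the text available.

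Protocol 12.3.3 makes this answer part of the safety result: "The number and percentage of patients with at least one adverse event will be summarized for all AEs, study product-related AEs, serious AEs", and also AEs leading to withdrawal. SAP 7.5.1 defines the count as "Drug-related AE (i.e. related or missing relationship with the IP"), with the same rule for drug-related SAEs. SAP 7.5.2 adds patient and event counts for "TEAEs by SOC, PT and relationship with IP". SAP section 8, which lists the changes from the protocol, contains nothing on causality.

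**The concern.** The two definitions set a high bar at each end and nothing covers the middle. If another factor could reasonably explain an event, but does not clearly do so, the event is too uncertain for RELATED and also too uncertain for NOT RELATED.

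Such events are foreseeable here. Protocol 3.4 expects mild irritation and short-lived burning or stinging as the product's risks. Protocol 8.1.2.7 grades burning/irritation and stinging/eye pain as symptoms of the disease, and Protocol 9.3.1.1 counts a worsening of the treated condition as an AE. Product effect and disease therefore overlap in the events most likely to be reported.

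Safety is the secondary objective, and the trial is open with a single arm. With no control rate to compare against, the investigator's answer is the only basis for attributing an event to the product. What is at stake is the number and percentage of patients with a drug-related AE or SAE, including whether the report can state that there were none.

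**Working it through.** The plan states no figure on this point, so there is none to reproduce. The check is of the wording, followed by a small illustration.

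**Step 1. Set the definitions against the SAP count.**

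| Investigator's view of the event | Meets RELATED? | Meets NOT RELATED? | SAP 7.5.1 drug-related count |
|---|---|---|---|
| Due to the product, no other reasonable explanation | Yes | No | Counted |
| Another condition clearly caused it | No | Yes | Not counted |
| Another condition could reasonably, but does not clearly, explain it | No | No | Counted if coded RELATED or left blank; not counted if coded NOT RELATED |

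The third row is the gap. The SAP's provision for a missing relationship covers only the blank field. It has no rule for an uncertain event that was coded NOT RELATED.

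**Step 2. Does the protocol recognise intermediate judgements elsewhere?** It does. Section 9.4 refers to events that may be linked to the product, 9.3.2.2 to a possible serious reaction, and 9.3.2.3 to suspected reactions. Section 3.4 describes an AE in an earlier NAAGA dry-eye study as "considered as possibly related to treatment". The two-answer scale cannot record that judgement.

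**Step 3. Size, by illustration.** Inputs: n = 55, the planned enrolment (Protocol 6.4), used as the denominator; the Wilson interval without continuity correction, z = 1.96 (SAP section 3). The counts of events are assumed.

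One patient moves the rate by 1/55 = 1.8 percentage points (with 50 patients, 1/50 = 2.0).

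Wilson limits are [2np + z² ± z√(z² + 4npq)] / [2(n + z²)], with z² = 3.8416 and denominator 2 × 58.8416 = 117.683.

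- 0/55: upper limit = (0 + 3.8416 + 1.96 × 1.96)/117.683 = 7.683/117.683 = 6.5%.
- 1/55: 2np = 2, q = 54/55 and √(3.8416 + 4 × 0.9818) = 2.787. The limits are (5.8416 ± 5.463)/117.683, that is 0.3% to 9.6%.

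| Assumed patients | All uncertain coded RELATED | All uncertain coded NOT RELATED |
|---|---|---|
| 0 clear, 1 uncertain | 1/55 = 1.8% (0.3 to 9.6) | 0/55 = 0% (0 to 6.5) |
| 1 clear, 1 uncertain | 2/55 = 3.6% (1.0 to 12.3) | 1/55 = 1.8% (0.3 to 9.6) |
| 1 clear, 2 uncertain | 3/55 = 5.5% (1.9 to 14.9) | 1/55 = 1.8% (0.3 to 9.6) |
| 1 clear, 4 uncertain | 5/55 = 9.1% (3.9 to 19.6) | 1/55 = 1.8% (0.3 to 9.6) |

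In each row the events are the same and only the coding differs.

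**The case against.** The strongest reply is that this is a wording gap with limited reach. Much of that reply stands.

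- **Direction.** A reader might infer that the bias can only run towards fewer related events. The documents do not support that. NOT RELATED is also strict, since the other cause must be clear, so an investigator could code an uncertain event either way. The RELATED wording, which names the patient's condition as a competing explanation, makes NOT RELATED the likely choice in dry-eye patients, but no more than likely.
- **Blanks.** A reader might also infer that a two-way choice rules out missing answers. It bars two answers, not none. Protocol 9.3.1.5 mentions an e-CRF, but 10.1 and 11.1.1 describe a paper form, which cannot force an entry. SAP 7.5.1 expects blanks and counts them conservatively.
- **Other safety data.** Protocol 9.3.2.1 records every AE whatever its relationship, so total AE and SAE counts are sound. Symptoms upon instillation are collected and tabulated separately, with no causality judgement (Protocol 9.1.4, SAP 7.1). The listings in SAP 7.5.3 show the investigator's opinion with details, so doubt about a single case may be visible there.
- **Incomplete text.** The NOT RELATED sentence is cut off and the CRF is not available. An instruction for uncertain cases cannot be excluded, but the two documents show none.
- **Pilot trial.** Safety is descriptive and no decision threshold depends on the drug-related rate.

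These points limit the consequence. They do not supply a category for the uncertain event.

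**Conclusion.** The concern holds in a limited form. As written, the categories in Protocol 9.3.1.5 are not exhaustive, and the SAP repairs only blank answers. Drug-related AE and SAE counts and the by-relationship tables can be understated to the extent that uncertain events are coded NOT RELATED.

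The documents give no frequency for such events, so 1.8 percentage points per patient is a unit of sensitivity, not an estimate of misclassification. It assumes a Safety set of 55. The conclusion also assumes that the missing end of the NOT RELATED sentence and the CRF contain no rule for uncertain cases.

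Two further inferences are tempting and should not be drawn:

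- **A rate from the earlier NAAGA study.** Protocol 3.4 reports two patients with AEs among 53 included, which invites a range of 0/53 to 2/53. The 53 are the whole study, the events are placed in the Naabak group, and the size of that group is not given. One event was a worsening of existing blepharitis, a concurrent disease that could itself meet NOT RELATED.
- **An effect on expedited reporting.** All SAEs go to the sponsor whatever their relationship (Protocol 9.3.2.1), and 9.3.2.3 speaks of suspected reactions without tying that term to the two categories. The link would be an inference.

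The point is worth correcting because the affected counts are planned safety results in a trial with no control arm, and the correction is small.

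**What to change.** In Protocol 9.3.1.5 and the CRF completion guidance:

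1. Define RELATED as at least a reasonable possibility of a causal relationship with the product.
2. Keep the NOT RELATED definition, and add that any event not meeting it is recorded as RELATED.

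The second line makes the categories exhaustive. SAP 7.5.1 and 7.5.2 need no change, and counting blanks as drug-related remains consistent with this rule.

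The cost is about two lines of wording. The reported drug-related rate may be slightly less favourable, because events with no clearly established other cause will now count as related.
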